## 5.5. Pharmacokinetic Parameter Estimation

Standard non-compartmental methods of analysis and model-based approaches using non-linear mixed effects modeling (NONMEM) or other appropriate software may be implemented to estimate PK parameters including maximum drug concentration ( $C_{max}$ ), area under the concentration curve during the dosing interval ( $AUC\tau$ ), half-life, clearance and volume of distribution after IV administration of LY3303560. Parameters such as time to  $C_{max}$  ( $t_{max}$ ),  $C_{max}$ , bioavailability, apparent clearance, apparent volume of distribution and half-life after SC administration may be reported. The accumulation ratio, expressed as either  $AUC\tau$  or minimum observed drug concentration ( $C_{min}$ ), following IV and SC routes may be reported.

When plotted Japanese and non-Japanese subjects will be identified in the same plot with different symbol types.

An analysis of the effect of dose, route of administration, concentration or demographic factors on the PK parameters may be conducted.

An analysis relating LY3303560 serum exposure versus LY3303560 CSF concentrations may be conducted.

### 5.5.1. Pharmacokinetic Statistical Inference

With just two doses no statistical inferential analyses will be carried out on PK parameters.

## 5.6. Imaging Analyses

### 5.6.1. Flortaucipir SUVr

Whilst the following proposed analyses are not intended to test any hypotheses, they will be carried out to estimate the extent of changes from baseline of the flortaucipir F 18 SUVr after treatment with LY3303560.

The data will be analysed by an Analyses of Covariance (ANCOVA). Fixed effects of treatment doses (LY3303560 and placebo) will be fitted and a baseline covariate adjustment will be used.

The primary comparison is between LY3303560 and placebo for change from baseline in composite SUVr at last flortaucipir F 18 imaging visit. Covariates such as (but not limited to) APOE status, MMSE baseline score, diagnosis and age may be explored.

The following SAS code may be utilized:

```
proc mixed data=tau_sim;
  class patient treatment;
  model change_from_baseline_SUVR_month12 = treatment baseline_SUVR APOE, MMSE_baseline
  diagnosis age / outp=resdat s cl solution residual;
  lsmeans treatment /pdiff cl alpha=0.05;
  ods output lsmeans=lsmean1 diffs=diff1 covparms=cov1;
run;
```

In addition to the ANCOVA analysis, a Bayesian posterior probability may be computed for each LY3303560 dose compared to placebo, it is essentially a Bayesian interpretation of the results assuming a non-informative prior. The credible interval will be computed for each dose relative to placebo. For each dose of LY3303560, the posterior probability that the SUVr difference to placebo is less than or equal to a certain value (X) will be calculated as the appropriate tail area in the t distribution, e.g.,  $\text{Prob}(\text{LY xmg} - \text{Placebo} \leq X) = \text{prob t}((X - d) / \text{sed}, \text{df})$  where d is the estimated difference, sed is the standard error of the estimated difference and df is the degrees of freedom associated with this difference. This Bayesian inference is justified on the assumption of vague priors for all parameters in the model. Values of interest for X may be a 0%, 10%, 30%, 50% and 100% reduction in accumulation of tau compared to placebo.

This analysis may be repeated for SUVrs in individual and other composite brain regions if needed.

Additional analyses may explore if there is an optimum baseline SUVr value that can be used as an inclusion criterion for future studies, i.e., do those with a higher baseline SUVr accumulate more tau burden over time and hence have high propensity to respond to treatment. To investigate this, the above analyses may be conducted on; all patients, patients with baseline SUVrs >1.05, SUVrs >1.1 and SUVrs >1.2. These cutoffs are subject to change based on data received and any analyses will consider the current literature and the in-house method study findings (A05 from AVID). Given the small sample sizes this is very exploratory and the findings may not be reported in the CSR.

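### SAP 5.6.1 explores a baseline-SUVr cutoff by re-fitting the treatment comparison in nested subsets, without a treatment-by-baseline term that would estimate whether response depends on baseline SUVr

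*SAP*

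**What the plan says.** SAP 5.6.1 fits an ANCOVA to change from baseline in composite SUVr: "Fixed effects of treatment doses (LY3303560 and placebo) will be fitted and a baseline covariate adjustment will be used". The contrast of interest is stated directly: "The primary comparison is between LY3303560 and placebo for change from baseline in composite SUVr at last flortaucipir F 18 imaging visit". The example SAS model statement begins "model change_from_baseline_SUVR_month12 = treatment baseline_SUVR APOE, MMSE_baseline" and goes on to diagnosis and age. All terms are main effects. The code requests the fixed-effect solution with confidence limits.

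A later paragraph of the same section looks for a baseline SUVr value that could serve as an entry criterion in future studies. The question is put as "do those with a higher baseline SUVr accumulate more tau burden over time and hence have high propensity to respond to treatment", and the method as "To investigate this, the above analyses may be conducted on; all patients, patients with baseline SUVrs >1.05, SUVrs >1.1 and SUVrs >1.2". On the thresholds it says "These cutoffs are subject to change based on data received", and adds that the literature and an in-house study will be considered. It closes with a caveat: "Given the small sample sizes this is very exploratory and the findings may not be reported in the CSR".

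No rule says when one cutoff would count as better than another or better than no cutoff. SAP 5.1.3 plans no multiplicity adjustment.

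**The concern.** The question has two halves. One is prognostic: do patients with higher baseline SUVr accumulate more tau? The other is predictive: do they respond more to treatment? The predictive half asks whether the LY3303560-minus-placebo difference varies with baseline SUVr. A model with treatment and baseline as main effects, re-fitted above a threshold, returns the treatment difference in that subset. It does not return how the difference changes with baseline.

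The reader must then judge by eye across four estimates, three of which come from subsets of the fourth. A smaller subset varies around the all-patient value by chance alone, and the plan gives no standard error for the gap between the two. The thresholds can also be revised after the data are seen.

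At stake is a design decision. A cutoff that looked better by chance could feed into eligibility for a later trial, possibly without appearing in the study report. A real dependence of response on baseline would have no estimate or interval attached to it.

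**Working it through.** The plan gives no error rate or power for this analysis, so there is no figure of its own to reproduce.

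**Inputs from the documents**
- 6 LY3303560 and 2 placebo patients per cohort (SAP 4.1), two cohorts, placebo pooled (SAP 5.1): 12 against 4.
- Model: change = treatment + baseline SUVr (SAP 5.6.1, further covariates left out).
- Three nested subsets compared with all patients.

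**Assumptions**
- The documents do not give the share of patients above 1.05, 1.1 and 1.2, so the shares are varied.
- A cutoff looks better if its estimated LY3303560-minus-placebo difference is more favourable than the all-patient estimate. The SAP does not state this rule.
- Null case: baseline SUVr affects neither change nor response.

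**Step 1, large-sample formula.** Let f be the share of patients above a cutoff. The gap between subset and all-patient estimates has variance proportional to 1/f − 1. For nested subsets with f_i > f_j, two such gaps have correlation r_ij = √[(1/f_i − 1)/(1/f_j − 1)]. The chance that at least one of three gaps is favourable is

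P = 1 − [1/8 + (asin r_12 + asin r_23 + asin r_13)/(4π)].

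For shares 0.90, 0.75 and 0.50, the values of 1/f − 1 are 0.111, 0.333 and 1. So r_12 = r_23 = √(1/3) = 0.577 and r_13 = √(1/9) = 0.333. The arcsines are 0.6155, 0.6155 and 0.3398, which sum to 1.571. Dividing by 4π gives 0.125, so P = 1 − 0.25 = 0.75. Across the shares tried, P runs from 0.59 (0.70/0.68/0.65) to 0.76 (0.95/0.85/0.60). Sample size does not enter the formula, so more patients would not remove the effect.

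**Step 2, simulation at 12 against 4.** Each cutoff taken singly looks better about half the time (0.47 to 0.54), as symmetry requires. At least one of three looks better as follows, among runs with a distinct subset that can be estimated:

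| Shares above the cutoffs | Proportion of trials |
|---|---|
| 0.90 / 0.75 / 0.50 | 0.71 |
| 0.80 / 0.65 / 0.45 | 0.71 |
| 0.75 / 0.50 / 0.25 | 0.67 |
| 0.60 / 0.40 / 0.20 | 0.63 |
| 0.80 / 0.75 / 0.70 | 0.60 |
| 0.98 / 0.95 / 0.90 | 0.58 |

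Counting runs without such a subset as not better lowers the last row to 0.47. Hence roughly 5 to 7 in 10.

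**Step 3, placebo patients per subset.** If baseline is unrelated to arm, a subset of 8 of the 16 patients holds 2 placebo patients on average. It holds at most one with probability [C(12,8) + 4·C(12,7)]/C(16,8) = (495 + 3168)/12870 = 0.28. For a subset of 6 of 16 the figure is [C(12,6) + 4·C(12,5)]/C(16,6) = (924 + 3168)/8008 = 0.51, and 924/8008 = 0.12 for none at all.

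**Step 4, the direct estimates (12 against 4, all patients).** Under the null, the 95% interval for an added treatment-by-baseline term excludes zero in 5.1% of trials, and that for the baseline slope of the additive model in 4.8%. For an interaction of 0.5 or 1.0 residual SD per baseline SD, the interaction interval excludes zero in about 10% or 26% of trials. For a common baseline slope of the same sizes, the slope interval does so in about 41% or 88%.

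**The case against.** The SAP makes this analysis optional, calls it very exploratory, disclaims hypothesis testing for the section, and says the cutoffs will be read with outside evidence. With about 4 placebo patients an interaction term will settle little, and a linear interaction does not locate a threshold. All of that stands and limits the consequence. It does not change which quantity the re-fits estimate, and the SAP's caveat about small samples does not address that.

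Three stronger readings are tempting and are not supported.

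- A reader might infer that the plan ignores accumulation altogether. It does not: the all-patient ANCOVA fits baseline SUVr and prints its coefficient. What is missing is a statement that this coefficient is the quantity to read.
- A reader might infer that a uniform drug effect would pass for evidence of a cutoff. The plan runs all patients alongside the subsets, so a uniform effect shows there too. In simulation with a uniform effect of 1 residual SD, the all-patient comparison is significant at 5% in 34–35% of trials and some subset in 24–32%. A subset is significant when all patients are not in only about 2–6% of trials, over effects of 0, 1 and 2 SD.
- A reader might set the 5-to-7-in-10 figure against the 5% for the interaction as if they were rival error rates. They are not. The first counts a larger point estimate, the second an interval that excludes zero. By the point-estimate standard, the interaction also favours high baseline in about half of null trials.

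The step from faster accumulation to greater response is also defensible as an assumption. SAP 5.6.1 expresses effects as percentage reductions in accumulation, and proportional slowing would give faster accumulators a larger absolute difference. There is no need to delete it.

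**Conclusion.** The concern holds in a limited form. The planned subset re-fits do not estimate whether the treatment difference changes with baseline SUVr, and no other output in SAP 5.6.1 does. Comparing overlapping subset estimates by eye will show some cutoff ahead of all patients in roughly 5 to 7 of 10 trials when baseline is irrelevant. That size rests on assumed shares above each cutoff and on reading better as a larger point estimate. On another reading it differs: judged by posterior probability of benefit under a true constant effect of 1 SD, the proportion was 0.43. The accumulation half of the question is already within reach of the planned model. The consequence is confined to an optional exploratory analysis and to any use made of it in designing later studies.

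**What to change.** In the paragraph of SAP 5.6.1 on an optimum baseline SUVr, make the main exploratory analysis the all-patient ANCOVA and report two quantities:

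1. The baseline SUVr coefficient with its 95% interval, as the accumulation estimate. Take it from the additive model: once an interaction is in the model, the coefficient describes the reference arm only.
2. An added treatment (LY3303560 pooled versus placebo) by continuous baseline SUVr term with its 95% interval, as the response estimate.

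Keep the results above 1.05, 1.1 and 1.2 as description only, and give the number of LY3303560 and placebo patients in each subset. No significance rule for adopting a cutoff is needed, in keeping with a study that plans no formal tests.

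The cost is a short wording change and one model term, with no new data. The drawback is a wide interaction interval (power about 10% to 26% in Step 4), so this study alone will probably not support a cutoff. The interval would at least show that openly.

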### **Early withdrawals**

It is anticipated that each patient has a baseline (screening) and week 51 value. All postbaseline scans from the screening scan will be considered to be included in the analyses. If the data suggest it is appropriate, a calculated annualized rate of change may be considered and analyses will be done with and without these dropouts included.

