- h The flortaucipir F 18 PET scan should be conducted at Visit 13 should the patient follow the 25-week treatment regimen or at Visit 19 for the 49-week treatment regimen. The flortaucipir F 18 PET scan should be completed at Visit 20 if the patient discontinues treatment after Visit 13 and before Visit 19. Patients permanently discontinued from study treatment due to initiation of a prohibited medication known to prolong the QT-interval should not have an ED flortaucipir F 18 scan unless the scan can be performed prior to initiation of the prohibited medication. Patients who have continued on study after introduction of a drug known to prolong QT interval (with sponsor approval) need a minimum of 14 days or 5 half-lives, whichever is longer, without that drug prior to the flortaucipir scan.
- i The baseline V2 LP will be performed no closer than 24 hours before first dose. Dosing may not proceed until patient has been at least 12 hours free of symptoms of post-LP headache, if present. Refer to Section 9.5.1 for details of sampling.
- j Coagulation test results should be reviewed before each LP. Concomitant medications should be reviewed to ensure that no changes to anticoagulation or antiplatelet therapy have occurred since the last coagulation test.
- k LPs are scheduled at either Visits 13, 19, 20, or early discontinuation. The corresponding coagulation test is required up to 2 weeks prior to the next scheduled LP.
- l The LP should be conducted at Visit 13 should the patient follow the 25-week treatment regimen or at Visit 19 for the 49-week treatment regimen. The LP should be completed at Visit 20 if the patient discontinues treatment after Visit 13 and before Visit 19.

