3.1. Study Rationale

Lilly is developing LY3303560 for the treatment of AD. This study (I8G-MC-LMDD [LMDD]) will be the second clinical study of LY3303560 and will evaluate the effects of repeated every 4 week (Q4W) administrations in patients over 6 months (7 doses), with the option of extending the treatment period up to 12 months (up to 6 further doses).

The study aims to assess the safety, tolerability, pharmacokinetics (PK), and pharmacodynamics (PD) of multiple doses of LY3303560 in patients with mild cognitive impairment (MCI) due to AD or mild to moderate AD. In this amendment (b), the higher dose cohorts of LY3303560 (700 and 1400 mg) have been removed based on an update to the PK/PD model originally used to predict the LY3303560 efficacious dose range. The ongoing single-dose I8G-MC-LMDA (LMDA) study is exploring single doses of LY3303560 up to 5600 mg. Future multiple-dose studies with LY3303560 will evaluate higher dose levels using a Q4W dosing regimen. In addition, the duration of dosing in the LMDD study has been reduced from 12 to 6 months, based on emerging longitudinal and baseline data using tau positron emission tomography (PET) imaging, which suggests that the study is now insufficiently powered to assess the effects of LY3303560 on progression of tau pathology using flortaucipir F 18 PET over 12 months (see [Appendix 6](#)).

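### SAP 5.6.1 expects a week-51 flortaucipir scan for every patient, but protocol (d) places the single follow-up scan at week 25 or week 49 for completers, and the SUVr ANCOVA has no term for the interval

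*SAP*

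**What the plan says.** **SAP 5.6.1.** The analysis target is: "The primary comparison is between LY3303560 and placebo for change from baseline in composite SUVr at last flortaucipir F 18 imaging visit". The sample code writes the response as "model change_from_baseline_SUVR_month12 = treatment baseline_SUVR APOE", followed by further covariates, none of them time. On adjustment the text says: "Covariates such as (but not limited to) APOE status, MMSE baseline score, diagnosis and age may be explored". Under the sub-heading Early withdrawals it says "It is anticipated that each patient has a baseline (screening) and week 51 value" and then "If the data suggest it is appropriate, a calculated annualized rate of change may be considered", with analyses run with and without the dropouts.

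**Protocol.** Section 3.1 records that "the duration of dosing in the LMDD study has been reduced from 12 to 6 months", and Section 5.1 offers an optional extension to 49 weeks. Section 9.4.7 plans two flortaucipir scans per patient. Section 2.2, footnote h, says the follow-up scan "should be conducted at Visit 13 should the patient follow the 25-week treatment regimen or at Visit 19 for the 49-week treatment regimen", and adds: "The flortaucipir F 18 PET scan should be completed at Visit 20 if the patient discontinues treatment after Visit 13 and before Visit 19". The follow-up schedule in Section 2.3 also lists an early-discontinuation scan. Section 10.3.3 and the synopsis plan SUVr summaries by treatment and visit, but name only baseline and Visit 13 or Visit 20. Visit 19 is absent.

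The SAP's Revision History says that Version 2 reflects amendments (b) and (d), and it describes the Visit 13 and Visit 19 scans. Section 5.6.1 was not brought into line.

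**The concern.** In the schedule, week 51 is Visit 20 on the 49-week track, and a scan is done there only if none was done at Visit 13 or 19. Nobody who completes either regimen as planned has a week-51 scan. For patients who extend, the discrepancy is only 14 days (Day 351 against Day 337). The scan that matters is the one at week 25, which covers about half the interval.

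Because the model uses raw change at whatever scan came last, the size of the estimated difference depends on how many patients extended. Extension is chosen after randomisation. Each dose is a single cohort while placebo is pooled across both (SAP 5.1), so a difference in uptake between cohorts would affect the dose contrasts as well as a difference between arms. At stake is how an exploratory SUVr estimate, and the posterior probabilities built on it, are read.

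**Working it through.** The documents contain no power or precision figure for this endpoint, so there is nothing to reproduce beyond the schedule. Dividing each day by 7 and rounding up recovers the protocol's week labels: Day 169 = week 25, Day 337 = week 49, Day 351 = week 51.

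**Inputs.** From the documents: Visit 13 on Day 169; Visit 19 on Day 337; baseline scan at Visit 2, nominally Day -8 and up to 28 days before dosing; 6 LY3303560 and 2 placebo patients per cohort, hence 4 pooled placebo. Assumed, because the documents give no values: linear accumulation of 1 unit per year, extension uptake p, and a residual SD of 0.1 to 1.0 units that is the same for both intervals.

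**Step 1: intervals.**
- Visit 13: (169 + 8)/365.25 = 177/365.25 = 0.485 years.
- Visit 19: (337 + 8)/365.25 = 345/365.25 = 0.945 years.
- Difference 0.460 years; ratio 345/177 = 1.95. A baseline scan on Day -28 gives 365/197 = 1.85, and one on Day -1 gives 338/170 = 1.99. Counting without a Day 0 shifts each interval by one day (0.482 and 0.942 years).
- Visit 20 after stopping in the extension: Day 351 gives (351 + 8)/365.25 = 0.98 years. If instead it falls 14 to 20 days after a last dose on Day 197 to 309, it lies between (197 + 14 + 8)/365.25 = 0.60 and (309 + 20 + 8)/365.25 = 0.92 years. The protocol can be read either way (see the objection).

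**Step 2: equal uptake.** Mean interval = 0.485 + 0.460p, which is 0.600, 0.715 and 0.830 years at p = 0.25, 0.5 and 0.75. With no drug effect every arm has the same mean change, so the bias is 0. With a true 30% slowing the raw difference is -0.180, -0.214 and -0.249. Divided by the placebo change, each is -30%.

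Variance is added: SD inflation = sqrt((p(1-p) x 0.46² + SD²)/SD²). At p = 0.5 this is 2.51, 1.36, 1.10 and 1.03 for SD 0.1, 0.25, 0.5 and 1.0.

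**Step 3: unequal uptake, no drug effect.** Bias = 0.46 x (LY3303560 uptake - placebo uptake) x annual accumulation.
- 3 of 6 LY3303560 and 0 of 4 placebo patients scanned at week 25: mean intervals 0.715 and 0.945; apparent reduction 1 - 0.715/0.945 = 24%.
- 3 of 6 LY3303560 and 4 of 4 placebo patients scanned at week 25: mean intervals 0.715 and 0.485; an apparent increase of 47%.
- Uptake 0.9 on placebo and 0.5 on LY3303560: 0.46 x (-0.4) = -0.18.
- Uptake 0.25 in one cohort and 0.75 in the other, placebo pooled at 0.5: 0.46 x (-0.25) = -0.115 for 70 mg and +0.115 for 210 mg.

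**Step 4: against sampling error.** In simulation (4 + 6 + 6 patients, scan dates varied by up to 7 days, ANCOVA on treatment and baseline), the 0.9 versus 0.5 case gave 95% intervals with coverage 0.84, 0.89, 0.93 and 0.945 at SD 0.1, 0.25, 0.5 and 1.0. At SD 0.5 to 1.0 the estimate's own SD is 0.35 to 0.69, against a bias of 0.18.

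**Step 5: annualised change.** Each change is divided by that patient's own interval. Under linear accumulation this gave bias 0 with no drug effect, and -0.30 per year for a true 30% slowing in every uptake scenario. Precision at equal uptake 0.5: the raw ANCOVA has SD 0.37 at residual SD 0.5, which is 0.37/0.715 = 0.52 per year, against 0.55 annualised. At residual SD 1.0 it is 0.69/0.715 = 0.97 against 1.11.

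**The case against.** Several points on the other side are sound.

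- **The target is not month 12.** A reader might infer that the SAP reports a pooled 12-month effect. The prose sets the comparison at the last imaging visit; the month-12 label is a variable name in code that is only offered for possible use. This stands. The problem is an undefined time scale, not a declared 12-month estimand.
- **No dilution on the SAP's own scale.** A reader might infer that a real effect is shrunk because -0.214 is smaller than the -0.283 (0.3 x 0.945) expected at week 49. The SAP's values of interest are percentage reductions in accumulation relative to placebo, and with equal uptake these are unchanged (Step 2). This stands.
- **The striking figures need a small SD.** The 2.51-fold inflation and 0.84 coverage assume SD 0.1. At that SD, 4 versus 6 patients would have about 98% power for a 30% slowing at week 49 (SE 0.065, 12 df), which sits badly with Protocol 3.1 calling the study insufficiently powered for tau progression over 12 months. At SD 0.5 and 1.0 that power is 13% and 7%. This stands.
- **Unequal uptake is hypothetical.** Patients and investigators are blinded, and nothing in the documents predicts a split by arm. This stands, although with 4 placebo patients a chance imbalance is easy.
- **Visit 20 may fall at week 51.** Protocol 2.3, footnote a, times follow-up relative to first dose, and Section 8.1 asks early stoppers to attend remaining visits where feasible. Together these can put the scan on Day 351. It is still not the expected time for each patient.
- **Remedies are already permitted.** By-visit summaries are planned, covariates are open-ended and an annualised rate may be considered. This stands only in part: the summaries omit Visit 19, scan interval is not named, and the annualised rate depends on the data and sits under early withdrawals. A patient who completes 25 weeks is not one.

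**Conclusion.** The concern holds in a limited form. SAP 5.6.1 is out of step with protocol (d) on when the follow-up scan happens. Its ANCOVA mixes intervals of about 0.48 and 0.94 years (ratio 1.95; 1.85 to 1.99 by baseline date), so the absolute estimate has no stated time scale.

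The documents do not show that a false effect will arise. That requires uptake to differ by arm or cohort, and uptake is not given. If it differs, the 24% example shows that the artefact can reach the size of the 10% and 30% reductions the SAP lists as of interest. That figure assumes linear accumulation and no drug effect. If the SD is at least half of annual accumulation, a bias such as 0.18 is a half to a quarter of the estimate's own SD, and sampling error dominates.

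No formal test is planned and the primary safety objective is untouched. This is a minor-to-moderate problem of interpretation.

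**What to change.** (a) In SAP 5.6.1, replace the week-51 sentence and the month-12 label with the Visit 13, Visit 19, Visit 20 and early-discontinuation schedule, and compute intervals from actual scan dates. Add Visit 19 to Protocol 10.3.3 and the synopsis.

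(b) Report SUVr change separately for week-25 and week-49 scans, with extension uptake by arm and by cohort.

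(c) Prespecify annualised change, per year from actual scan dates, for all patients and not only early withdrawals, alongside the raw-change ANCOVA. State that it assumes linear accumulation and does not remove selection into the extension.

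The cost is SAP wording, one extra prespecified estimate, and one line each in Protocol 10.3.3 and the synopsis. No new data are needed. Annualising makes week-25 changes noisier: on a per-year scale the SD rises from about 0.52 to 0.55 at residual SD 0.5, and from about 0.97 to 1.11 at residual SD 1.0.
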